## 1.2 Study Population

### 1.2.1 Inclusion Criteria

- Adult patients with acute respiratory failure receiving invasive mechanical ventilation at Duke University Medical Center, managed in pressure-support mode of ventilation

### 1.2.2 Exclusion Criteria

- Actively undergoing a spontaneously awakening trial (SAT)
- Patient or surrogate unable to provide informed consent
- Currently pregnant
- Currently incarcerated
- Acute exacerbation of an obstructive lung disease
- Known esophageal varices or any other condition for which the attending physician deems an orogastric catheter to be unsafe
- Esophageal, gastric, or duodenal surgical procedure(s) within the last 6 months

### 1.2.3 Data Acquisition

Study design	Prospective cohort study
Data source/how the data were collected	Data entered directly into REDCap by study staff
Contact information for team member responsible for data collection/acquisition	[name]
Date or version (if downloaded, provide date)	February 22, 2024
Data transfer method and date	Downloaded directly from REDCap
Where dataset is stored	BiostatsCore\CRU\Pulmonary\[name]\Pro00106860 ASOP\Data\

## 1.3 Outcomes, Exposures, and Additional Variables of Interest

### 1.3.1 Maneuver Variables

Maneuver	Variable(s)	Description	Specifications

A	dprs_servo[1-5]	Static Respiratory System Driving Pressure from Ventilator	Calculated within REDCap as: pplat_servo_a[1-5] - peep_vent_a[1-5]
B	p0_1_[1-5]	P 0.1 from Servo	Entered directly into REDCap
C	paw_max_b[1-5]	Max Airway Pressure	Entered directly into REDCap
	peep_vent_b[1-5]	PEEP from Ventilator	Entered directly into REDCap
	aop_[1-5]	Airway Occlusion Pressure	Calculated within REDCap as: peep_vent_c[1-5] - max_neg_paw[1-5]
	pred_delta_pl_[1-5]	Predicted $\Delta P_L$	Calculated as: paw_max_b[1-5] - peep_vent_b[1-5] + (2/3)*aop_[1-5]
D	dprs_stat_vc_d[1-5]	Static Respiratory System Driving Pressure	Calculated within REDCap as: pplat_aw_d[1-5] - peep_vent_d[1-5]

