- Dynamic change in airway pressure (“occlusion pressure”) and transpulmonary pressure during an airway occlusion maneuver during a pressure support breath
- Respiratory effort as measured by the ventilator p(0.1).
- Change in tidal volume with a decrease in set pressure-support
- Change in airway and transpulmonary plateau pressure with decreased pressure support
- Change in airway and transpulmonary driving pressure with decreased pressure support

Data collected from the EHR after study specific measurements will include

- Total duration of mechanical ventilation in days
- Total duration of intensive care length of stay in days
- Total duration of hospital length in stay in days
- Survival to discharge

No data will be collected after the patient is discharged from the hospital.

8. Randomization

This is a cohort study and there will be no randomization of patients to a treatment or control. Due to possible bias based of order of methods assessed, we will randomize the order that each patient is tested, including the gold standard (A) and the three methods of interest (B, C and D). Randomization schema will be a simple randomization of the methods for each patient, where each patient will be assessed on all 4 methods. A list of method order will be created prior to study start with order consisting of (e.g. ABCD, BCDA, CDAB, etc).

9. ASOP procedures.

ASOP is a prospective cohort study comparing three methods for assessing risk of self-induced lung injury to a gold-standard measurement in patients with acute respiratory failure being managed with pressure-support ventilation.

The study will compare the following four methods for assessing risk for SILI during PSV:

1. The transpulmonary plateau and driving pressure during a volume control. This will be considered the gold standard measurement of both plateau and driving pressure.
2. The airway plateau and driving pressure during a volume control breath.
3. The airway plateau and driving pressure during a pressure support breath
 - a. This variable will be measured in two ways. Once using an inspiratory hold on the Servo ventilator, and once using a Resironics NM3 device with VentAssist SoftWare.
4. The dynamic change in airway pressure and transpulmonary pressure during an end expiratory occlusion maneuver during a pressure support breath.

After enrollment, all baseline ventilator settings will be recorded (including PEEP, pressure support, tidal volume, and FiO2).

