- ix) Calculate transpulmonary driving pressure from ventilator and esophageal balloon ([a.4-a.5]-[a.1-a.3]) for each recorded breath
- x) Record P(0.1) from ventilator for 5 breaths (a.10)

b) Measure dynamic respiratory system driving pressure (DPrs-dyn) and transpulmonary driving pressure (DPtp-dyn)

- i) Record PEEP from ventilator (b.1)
- ii) Record PEEP from NM3 monitor (b.2)
- iii) Record end-expiratory esophageal pressure during a breath (b.3)
- iv) Record maximum airway pressure (b.4)
- v) Record maximum inspiratory esophageal pressure (b.5)
- vi) Record Airway plateau pressure from NM3 monitor (b.6)
- vii) Repeat for 5 total measurements of each variable
- viii) Calculate dynamic driving pressure across the respiratory system (DPrs-dyn) (b.7 = b.4-b.1)
- ix) Calculate dynamic transpulmonary driving pressure (DPtp-dyn) (b.8 = ([b.4-b.5]-[b.1-b.3]))
- x) Calculate the dynamic driving pressure across the respiratory system from the NM3 monitor DPrs-Dyn-NM3 (b.6-b.2)

c) Measure airway occlusion test (AOC)

- i) Measure PEEP (c.1)
- ii) Measure end expiratory esophageal pressure (c.2)
- iii) Perform expiratory hold
 - (1) Expiratory hold should be held for entirety of respiratory effort until airway pressure returns to baseline
 - (a) Measure maximum negative deflection of airway pressure (c.3)
 - (b) Measure maximum negative deflection of esophageal pressure (c.4)
- iv) Repeat 5 total measurements of each variable
- v) Calculate airway occlusion pressure (AOC = c.1-c.3) for each breath

d) Measure static respiratory system (DPrs-vc) and transpulmonary driving pressure (DPtp-vc) in volume control breath

- i) Change ventilator mode to SIMV (PSV+VC), with IMV breaths set in Volume control.
 - (1) Set PSV settings identical to baseline settings recorded in section 2.
 - (2) For VC breaths, volume set to average tidal volume calculated in section 2. subsection D.
 - (3) Set rate of IMV breaths to 1/min
 - (4) Set flow rate for VC breaths to minimum
- ii) Measure PEEP (d.1)
- iii) Measure end-expiratory esophageal pressure (d.2)
- iv) Measure airway plateau (d.3) during inspiratory hold
- v) Measure end-inspiratory esophageal pressure (d.4) during inspiratory hold
- vi) Repeat for 5 total measurements of each variable
- vii) Calculate respiratory system driving pressure (DPrs-vc = d.2-d.1)
- viii) Calculate transpulmonary plateau pressure (d.6 = d.2-d.4)

- ix) Calculate driving pressure across the lung ($DP_{tp-vc} = d.6 - (d.1-d.3)$)

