### 1.1.1 Study Aims

1. Determine the internal consistency of four methods of measuring airway plateau pressure during pressure-support ventilation, utilizing:
  - a. The static respiratory driving pressure from ventilator in pressure support during inspiratory hold (Maneuver A; considered the gold-standard measurement)
  - b. The lung driving pressure in pressure support during first 0.1 seconds of inhalation (Maneuver B)
  - c. The occlusion pressure in pressure support (Maneuver C)
  - d. The static respiratory system driving pressure in volume control (Maneuver D)
2. The pairwise consistency of measures (AB, AC, AD, BC, BD, CD)

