## 1.4 Statistical Analysis Plan

### 1.4.1 Demographic and Clinical Characteristics (“Table 1”)

The variables listed in Section 3.2 will be summarized for the cohort using mean with standard deviation, median with 25th and 75th percentiles (Q1, Q3), and min-max for continuous measures, and frequency with percentage for categorical measures.

### 1.4.2 Analyses Plan for Aim 1

The internal consistency of the static respiratory driving pressure (DPRS), that is to say the consistency of DPRS measures from the same patient, will be quantified for each maneuver (A, B, C, and D) separately using the intraclass correlation coefficient (ICC). The ICC measures the correlation of two observations coming from the same patient.

Specifically, the ICC is defined as

$$ICC = \frac{\sigma_{\alpha}^2}{\sigma_{\alpha}^2 + \sigma_{\epsilon}^2}$$

Where  $\sigma_{\alpha}^2$  is the variation in DPRS measurements between different patients, and  $\sigma_{\epsilon}^2$  gives the within-patient variation of DPRS measurements, with the sum  $\sigma_{\alpha}^2 + \sigma_{\epsilon}^2$  giving the total variation in DPRS values across all patients. Therefore, the ICC measures the proportion of total variation in the DPRS measurements that is due to variation between patients.

95% confidence intervals for each of the within-patient and between-patient variances, as well as the ICC, will be calculated using the empirical 2.5th and 97.5th percentiles of 10,000 parametric bootstrap replications.

General guidelines for interpretation of ICC values are as follows (Cicchetti, 1994):

- <0.40: poor consistency
- 0.40-0.59: fair consistency
- 0.60-0.74: good consistency
- 0.75-1.00: excellent consistency

Technical details:

The values of  $\sigma_{\alpha}^2$  and  $\sigma_{\epsilon}^2$  will be estimated from a linear mixed-effects model, with

$$Y_{ij} = \mu + \alpha_i + \epsilon_{ij}$$

With  $Y_{ij}$  being the  $j$ th DPRS measurement from the  $i$ th patient, with up to 5 measurement each from the 15 patients enrolled.

Here, the underlying mean DPRS value is  $\mu$  and the subject-specific deviation from the overall mean is given by  $\alpha_i$  for the  $i$ th patient, and the within-patient variation of measurements is given by  $\epsilon_{ij}$ .

We assume that

$$\alpha_i \sim N(0, \sigma_\alpha^2), \epsilon_{ij} \sim N(0, \sigma_\epsilon^2)$$

With  $\alpha_i$  and  $\epsilon_{ij}$  each iid and independent of each other.

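### Maneuver C is a predicted lung pressure, yet the SAP labels it DPRS, pairs it with respiratory-system pressures, and never compares it with measured transpulmonary pressure

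*SAP*

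**What the plan says.** **Definition of C.** SAP 1.3.1 gives the maneuver C result as "paw_max_b[1-5] - peep_vent_b[1-5] + (2/3)*aop_[1-5" (closing bracket cut off here), under the description of a predicted ΔP_L. It combines maximum airway pressure and PEEP from protocol step 5b with the airway occlusion pressure (AOP) from step 5c.

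**Definition of A and D.** The same table defines A as "pplat_servo_a[1-5] - peep_vent_a[1-5" and D as "pplat_aw_d[1-5] - peep_vent_d[1-5". Both are static respiratory-system driving pressures.

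**How they are analysed.** SAP 1.4.2 assigns one quantity to every maneuver: "The internal consistency of the static respiratory driving pressure (DPRS". SAP 1.1.1 lists the second aim as "The pairwise consistency of measures (AB, AC, AD, BC, BD, CD", names A as the gold standard, and describes all four maneuvers as ways of measuring airway plateau pressure. SAP 1.4.3 estimates ρ_inter for each pair. The only Bland-Altman plot, in SAP 1.4.4, is A against D.

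**What the protocol collects.** Protocol section 9 names as its reference "The transpulmonary plateau and driving pressure during a volume control" breath. Esophageal pressure is recorded in steps 5a to 5e. Step 5b, the source of C's maximum airway pressure, also instructs staff to "Calculate dynamic transpulmonary driving pressure (DPtp-dyn", item b.8). No esophageal or transpulmonary variable appears in SAP 1.3.1 or in any SAP analysis.

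**The concern.** The protocol's specific aim is to see whether techniques using only airway pressure, including the occlusion test, give results similar to transpulmonary pressure. C is the one analysed variable built to estimate a lung pressure. The SAP compares it with two respiratory-system pressures and with P0.1 (maneuver B), but not with the lung pressure measured in the same patients.

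If C and its comparator have different true values, a low coefficient may reflect that difference and not a fault in the occlusion method. A high coefficient would not show that C predicts lung stress either. The validity question for this method is left unanswered, although every patient has a balloon catheter placed so that it can be answered.

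**Working it through.** The plan gives no agreement figure, SD or lung fraction to reproduce. The check is therefore algebra on the documents' formulas, followed by illustrations on stated assumptions.

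**1. Static lung versus respiratory-system pressure (protocol step 5a).** DPrs = a.4 − a.1 and DPtp = (a.4 − a.5) − (a.1 − a.3). Hence DPrs − DPtp = a.5 − a.3, the change in esophageal pressure from end-expiration to the hold. The two are equal only if that change is zero.

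**2. Peak versus plateau.** With PEEP the same in both steps, C − A = (b.4 − a.4) + (2/3)·AOP. The first term is maximum airway pressure minus plateau pressure. C therefore differs from A in being dynamic as well as in being a lung pressure.

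**3. What reaches ρ_inter.** In the SAP 1.4.3 model β_j is a fixed method effect and is not in the denominator, so a constant offset leaves ρ_inter unchanged. Patient-specific differences go into γ_ij and lower it. With no measurement error, and taking the variance of γ_ij as the σ_γ² in the SAP's definition of ρ_inter, ρ_inter = 2·Cov(Y₁,Y₂) / (Var Y₁ + Var Y₂).

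**4. Error-free illustrations.** Assumed, not in the documents: DPrs D with mean 12 and SD 3 cmH2O; lung pressure rD, with r independent of D.

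- Constant offset: 1.00.
- Constant ratio r: 2r/(1 + r²). For r = 0.7 this is 1.4/1.49 = 0.94.
- r mean 0.70, SD 0.10: Var(rD) = 0.50 × 153 − 8.4² = 76.50 − 70.56 = 5.94; Cov = 0.7 × 9 = 6.3; ρ = 12.6/14.94 = 0.84.
- r mean 0.70, SD 0.15: Var(rD) = 0.5125 × 153 − 70.56 = 7.85; ρ = 12.6/16.85 = 0.75.
- r mean 0.60, SD 0.10: Var(rD) = 0.37 × 153 − 7.2² = 4.77; Cov = 5.4; ρ = 10.8/13.77 = 0.78.
- r mean 0.70, SD 0.10, plus an independent peak-versus-plateau term of mean 4, SD 2 cmH2O: ρ = 12.6/(9 + 5.94 + 4) = 12.6/18.94 = 0.67.
- Chest-wall part varying independently of the lung part, SD 1 cmH2O: 8/8.5 = 0.94. With SD 1.5: 6.75/7.875 = 0.86.

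For the 0.67 case, simulation with error-free data gave a central 95% sampling range of 0.25 to 0.88 for the SAP's 15 patients and 0.37 to 0.84 for the protocol's 25.

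**5. The like-for-like comparison.** b.8 = (b.4 − b.5) − (b.1 − b.3), so C − b.8 = (2/3)·AOP − (b.3 − b.5). This is zero when the prediction is perfect. C and b.8 share (b.4 − b.1), however, and that inflates a correlation-type index. With an assumed shared-term SD of 4 and wholly unrelated effort terms of SD 2, ρ = 16/(16 + 4) = 0.80 with no predictive value at all. The shared term cancels in the difference.

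**6. DPtp-vc as printed.** Step 5d records d.1 PEEP, d.2 end-expiratory esophageal pressure, d.3 airway plateau and d.4 end-inspiratory esophageal pressure. It then calculates DPrs-vc as d.2 − d.1, transpulmonary plateau as d.2 − d.4, and DPtp-vc as d.6 − (d.1 − d.3). In all three, d.2 and d.3 are interchanged. SAP 1.3.1 uses plateau minus PEEP for D, so D itself is unaffected.

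**The case against.** Several points on the other side stand.

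- **Comparing unlike quantities is partly by design.** The protocol itself sets airway-only methods against a transpulmonary reference. That supports restoring the reference; it does not support replacing it with A.
- **The SAP is already restrained about C.** SAP 1.3.1 labels the variable correctly, Bland-Altman is confined to the two static respiratory-system pressures, and C gets only ρ_inter, plots of patient means and summaries. DPRS in SAP 1.4.2 may be loose shorthand, since it also covers B, which is P0.1. Even so, Aim 2 is framed as consistency between methods, and C has no comparison with a lung pressure.
- **No failure rule exists.** The interpretation bands stand under Aim 1, Aim 2 sets no threshold, and the protocol calls the study descriptive. That a low A–C value would be read as failure is an inference about readers.

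Two stronger readings are tempting. A reader might infer that error-free measurements must give a low coefficient, or that 0.84 is a true ceiling. The documents support neither. The figure depends on an assumed lung fraction independent of DPrs, other structures give 0.86 to 1.00, and the lung-fraction values of 0.75 to 0.84 lie in or at the edge of the SAP's top band. A reader might also infer a mean gap of 3.6 cmH2O (0.3 × 12) or 4.8 cmH2O (0.4 × 12), with C below A. That ignores C's peak-pressure term: adding a mean of 4 turns −3.6 into +0.4, so the sign is not established. In any case β_j keeps a mean gap out of ρ_inter.

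**Conclusion.** The point holds in this form. C is a predicted dynamic lung pressure change. The SAP groups it under DPRS, pairs it with static respiratory-system pressures, and never compares it with the transpulmonary pressure that the protocol collects and names as reference. This much follows from the documents' own formulas and needs no assumption. As a result, A–C and C–D cannot separate method error from a difference in quantity, and cannot show whether the occlusion method predicts lung stress.

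The size of the effect on ρ_inter is not known. It depends on between-patient variation that the documents do not give, and the illustrations above show a range, not an estimate. The change should be made because the trial's stated question for this method is otherwise unanswered, not because a particular coefficient can be forecast.

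**What to change.** 1. In SAP 1.1.1, 1.3.1 and 1.4.2, call C predicted ΔPL throughout and stop grouping it under DPRS.
2. In SAP 1.4.3, describe A–C and C–D as association between different quantities, not agreement.
3. In SAP 1.4.4, add a Bland-Altman analysis of pred_delta_pl minus measured DPtp-dyn (b.8), which is the same as (2/3)·AOP against the esophageal swing (b.3 − b.5). Use patient means, because AOP and b.8 come from different breaths. Do not rely on ρ_inter for this pair, because both variables contain (b.4 − b.1).
4. Add C against DPtp-vc as the comparison with the protocol's reference, noting that DPtp-vc is static and taken in volume control.
5. Before either comparison, confirm how b.5, described as a maximum inspiratory esophageal pressure, was recorded, since b.8 depends on it. Derive DPtp-vc as (airway plateau − end-inspiratory esophageal pressure) − (PEEP − end-expiratory esophageal pressure), and correct the printed step 5d formulas.
6. Date the addition and label it as made after the February 22, 2024 data download given in SAP 1.2.3.

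The cost is SAP wording and code, once the esophageal variables are confirmed to be in the REDCap download. No new measurement is needed.

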### 1.3.2 Demographic and Clinical Characteristics

Variable	Description	Variables and Source	Specifications
Sex	Patient sex	sex	
 
1. Male
 
2. Female
 

Ethnicity	Patient ethnicity	ethnicity	
 
1. Not Hispanic or Latino
 
2. Hispanic or Latino
 
3. Unknown or Not Reported
 

Race	Patient race	race	
 
1. White
 
2. Black
 
3. Asian
 
4. Native American or Alaska Native
 
5. Native Hawaiian or Pacific Islander
 
6. More than one race
 
7. Unknown or Not Reported
 

Age at intubation	Patient age at intubation	Derived from dob and date_study	
Days of ventilation	Days of mechanical ventilation	mv_days	

Height	Patient height (cm)	height	
Weight	Patient weight (kg)	weight	
BMI	Patient BMI	bmi	
Ideal body weight	Patient ideal body weight	ibw	
 
Male: <math>50 + .91 * \text{height} - 152.4</math>
 
Female: <math>45 + .81 * \text{height} - 152.4</math>
 

cc/Kg	6 cc/kg of ideal body weight	cc_kg	$6 * \text{ibw}$
Admission diagnosis	Admission diagnosis/cause of respiratory failure	admit_diag, other_cause_admisison	
 
ARDS
 
Post-surgical
 
Trauma
 
Heart-Failure
 
Cardiac Arrest
 
Stroke
 
Other
 

APACHE II Score	Total APACHE II score	ap2_total_score	
APACHE II Classification	Interpretation of APACHE II score	ap2_interpretation	
 
0-4: 4% death rate
 
5-9: 8% death rate
 
10-14: 15% death rate
 
15-19: 25% death rate
 
20-24: 40% death rate
 
25-29: 55% death rate
 
30-34: 75% death rate
 
>34: 85% death rate
 

## 1.4 Statistical Analysis Plan

### 1.4.1 Demographic and Clinical Characteristics (“Table 1”)

The variables listed in Section 3.2 will be summarized for the cohort using mean with standard deviation, median with 25th and 75th percentiles (Q1, Q3), and min-max for continuous measures, and frequency with percentage for categorical measures.

### 1.4.2 Analyses Plan for Aim 1

The internal consistency of the static respiratory driving pressure (DPRS), that is to say the consistency of DPRS measures from the same patient, will be quantified for each maneuver (A, B, C, and D) separately using the intraclass correlation coefficient (ICC). The ICC measures the correlation of two observations coming from the same patient.

Specifically, the ICC is defined as

$$ICC = \frac{\sigma_{\alpha}^2}{\sigma_{\alpha}^2 + \sigma_{\epsilon}^2}$$

Where  $\sigma_{\alpha}^2$  is the variation in DPRS measurements between different patients, and  $\sigma_{\epsilon}^2$  gives the within-patient variation of DPRS measurements, with the sum  $\sigma_{\alpha}^2 + \sigma_{\epsilon}^2$  giving the total variation in DPRS values across all patients. Therefore, the ICC measures the proportion of total variation in the DPRS measurements that is due to variation between patients.

95% confidence intervals for each of the within-patient and between-patient variances, as well as the ICC, will be calculated using the empirical 2.5th and 97.5th percentiles of 10,000 parametric bootstrap replications.

General guidelines for interpretation of ICC values are as follows (Cicchetti, 1994):

- <0.40: poor consistency
- 0.40-0.59: fair consistency
- 0.60-0.74: good consistency
- 0.75-1.00: excellent consistency

Technical details:

The values of  $\sigma_{\alpha}^2$  and  $\sigma_{\epsilon}^2$  will be estimated from a linear mixed-effects model, with

$$Y_{ij} = \mu + \alpha_i + \epsilon_{ij}$$

With  $Y_{ij}$  being the  $j$ th DPRS measurement from the  $i$ th patient, with up to 5 measurement each from the 15 patients enrolled.

Here, the underlying mean DPRS value is  $\mu$  and the subject-specific deviation from the overall mean is given by  $\alpha_i$  for the  $i$ th patient, and the within-patient variation of measurements is given by  $\epsilon_{ij}$ .

We assume that

$$\alpha_i \sim N(0, \sigma_\alpha^2), \epsilon_{ij} \sim N(0, \sigma_\epsilon^2)$$

With  $\alpha_i$  and  $\epsilon_{ij}$  each iid and independent of each other.

### 1.4.3 Analyses Plan for Aim 2

For each pair of maneuvers, the consistency of the measures between the two methods will be quantified using the interclass correlation coefficient  $\rho_{inter}$ .

$\rho_{inter}$  gives the correlation between any two measurements from the same patients from different methods.

Similarly to Aim 1, the  $\rho_{inter}$  is defined as

$$\rho_{inter} = \frac{\sigma_\alpha^2}{\sigma_\alpha^2 + \sigma_\gamma^2 + \sigma_\epsilon^2}$$

95% confidence intervals for each of the variances, as well as the ICC, will be calculated using the empirical 2.5th and 97.5th percentiles of 10,000 parametric bootstrap replications.

For each maneuver, the within-subject mean values will be calculated. For each pair of maneuvers (A and B, A and C, etc) the subject-level mean values will be plotted.

Summaries of the subject-level mean and standard deviations will be reported using mean with standard deviation, median with first and third quartiles, and range, stratified by maneuver.

Technical details:

The values for  $\sigma_\alpha^2, \sigma_\gamma^2, \sigma_\epsilon^2$  are estimated from the linear mixed effects-model

$$Y_{ijk} = \mu + \alpha_i + \beta_j + \gamma_{ij} + \epsilon_{ijk}$$

Where  $Y_{ijk}$  is the  $k$ th measurement coming from the  $i$ th patient using method  $j$ .

Here,  $i$  indexes the 15 patients,  $j$  indexes the either the first or second of the two methods (A or B, A or C, etc), and  $k$  indexes the breath number for patient  $i$  on method  $j$ . Because some measurements were discarded, each patient on each method has up to, but sometimes less than, 5 repetitions.

The various terms represent:

- $\mu$  = the overall mean value for method 1
- $\alpha_i$  = the subject-specific deviation from the overall mean for method 1
- $\mu + \alpha_i$  = the subject-specific mean for method 1
- $\beta_j$  = the deviation in the overall mean for method 2 from method 1
- $\mu + \beta_j$  = the overall mean for method 2
- $\gamma_{ij}$  = the subject-specific interaction term for method 2 (relative to the subject-specific deviation for method 1)
- $\alpha_i + \gamma_{ij}$  = the subject-specific deviation from the overall mean for method 2

We assume that

$$\alpha_i \sim N(0, \sigma_\alpha^2), \quad \gamma_{ij} \sim N(0, \sigma_\alpha^2), \quad \epsilon_{ijk} \sim N(0, \sigma_\epsilon^2)$$

With  $\alpha_i$ ,  $\gamma_{ij}$ , and  $\epsilon_{ijk}$  each iid and mutually independent of each other.

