- e) Measure change in airway plateau pressure and patient effort with decrease in Pressure-support.
 - i) Ventilator will be returned to baseline settings
 - ii) The set pressure support will be decreased by 5 cm of H₂O (to a minimum of 5 cm of H₂O)
 - iii) The new tidal volume will be recorded (e.1)
 - iv) Measure PEEP (e.2)
 - v) Measure end-expiratory esophageal pressure (e.3)
 - vi) Perform and inspiratory hold in pressure-support
 - (1) Measure airway plateau pressure (e.4)
 - (2) Measure end-inspiratory esophageal pressure (e.5)
 - vii) Measure a P(0.1) (e.6)
 - viii) Repeat for 5 total measurements of each variable
- ix) Calculate new static respiratory system driving pressure (DP_{rs-new}) (e.7=e.4-e.2)
- x) Calculate new transpulmonary driving pressure (DP_{l-new}) (e.8=[e.4-e.5]-[e.2-e.3])
- f) Return all ventilator settings to baseline.

The order of performing these measurements will be randomized to minimize bias of the order of measurements.

All study specific measurements and maneuvers will be completed in one day. After completion of study measurements and maneuvers, the orogastric balloon will be removed.

A patient's EHR will be monitored until hospital discharge to collect previously mentioned study specific endpoints as described above.

Overall, we plan to enroll 25 patients.

10. Statistical design, analyses, sample size, and power

Statistical Design and Analysis Plan

Patient and clinical characteristics will be described overall using frequency and percent for categorical characteristics, and mean, standard deviation, median, and quartiles for continuous variables. Agreement statistics such as the intraclass correlation coefficient (ICC), Bland-Altman plots, and Cohen's kappa, will be used to assess agreement of measures between the gold-standard and the three methods of interest. A mixed-effects regression model will be used to determine the difference between each method and the gold-standard taking into account the randomization order with results presented as the least squares mean (LSM) difference with 95% confidence interval (CI). All analyses will be performed using SAS 9.4 (Cary, NC) and a p-value <0.05 will be considered statistically significant.

Sample Size and Power

This is a descriptive study. The 25-person sample size reflects the pragmatics of recruitment with available study staff and should provide adequate power to evaluate similarities given that each patient acts as his/her own control.

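### SAP 1.4.3 plans no confidence interval for any mean difference between methods and no order adjustment, although protocol section 10 specifies both

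*SAP*

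**What the plan says.** **Protocol.** Section 10 states: "A mixed-effects regression model will be used to determine the difference between each method and the gold-standard taking into account the randomization order". The result is to be given as a least squares mean difference with a 95% CI. Section 8 gives the reason for randomising order: "Due to possible bias based of order of methods assessed, we will randomize the order that each patient is tested". Section 9 repeats it: "The order of performing these measurements will be randomized to minimize bias of the order of measurements". The reference in section 9 is transpulmonary plateau and driving pressure during a volume-control breath. The central hypothesis in section 3 is that the three airway-based techniques give results similar to that reference.

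**SAP 1.4.3 (Aim 2).** The section opens: "For each pair of maneuvers, the consistency of the measures between the two methods will be quantified using the interclass correlation coefficient". The inferential quantity for each pair is thus ρ_inter = σ_α² / (σ_α² + σ_γ² + σ_ε²). On intervals it says: "95% confidence intervals for each of the variances, as well as the ICC, will be calculated". The model is Y_ijk = μ + α_i + β_j + γ_ij + ε_ijk, indexed by patient, method and breath. β_j is defined as "the deviation in the overall mean for method 2 from method 1", but no estimate or CI for it is listed as output. The remaining outputs are descriptive. Subject-level means are plotted for each pair, and there is a table by maneuver: "Summaries of the subject-level mean and standard deviations will be reported using mean with standard deviation", with quartiles and range.

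**SAP 1.4.4.** One Bland-Altman plot is planned, for A and D. Its band is the mean difference ± 1.96 SD of the differences, and the text presents this as the ordinary 95% CI for the mean difference.

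**SAP 1.1.1 and 1.3.1.** Maneuver A, an airway driving pressure in pressure support, is named as the gold standard. No listed variable uses esophageal pressure, and none records the sequence.

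**The concern.** Whether two methods give similar results depends on how far apart they are on average as well as on how well they rank patients. ρ_inter addresses only the second part. A pair could have a high ρ_inter, and be called excellent if the scale in SAP 1.4.2 is carried over, while one method reads several cmH2O above the other. The protocol covered this with a mean difference and its CI. In the SAP the difference has no planned interval, so the central hypothesis has no stated precision.

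The protocol also randomised order because it thought order might matter, and it said the analysis would account for it. The SAP analysis does not use the order.

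Finally, the wording in 1.4.4 could lead a reader to take the limits of agreement for the missing CI.

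**Working it through.** The documents give no SD, margin or power, so there is no stated figure to reproduce. N is 15 in SAP 1.4.2 and 1.4.3, with up to 5 breaths per method. All SDs below are assumptions for illustration.

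**1. Protocol against SAP**

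| Item | Protocol sections 8-10 | SAP 1.1.1, 1.3.1, 1.4.3, 1.4.4 |
|---|---|---|
| Reference | Transpulmonary, volume control | Maneuver A: airway, pressure support |
| Inferential quantity | Mean difference from reference | ρ_inter for each pair |
| 95% CI | For the difference | For the variances and ρ_inter |
| Order | Taken into account | No term, no variable |

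**2. ρ_inter and a constant offset.** β_j does not appear in the formula, so no constant shift can alter ρ_inter. This is algebra and needs no assumed SD. As an illustration, one simulated dataset was used (15 patients, 2 methods, 5 breaths; assumed SDs of 4, 1 and 1 cmH2O for α, γ and ε). Method 2 was shifted by 0, 2, 5 and 10 cmH2O:
- Estimated ρ_inter was 0.709 each time.
- The mean difference was 0.36, 2.36, 5.36 and 10.36, each ± 0.98 (95% CI half-width).

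**3. The 1.4.4 band against a CI for the mean.** Let S be the SD of the 15 subject-mean differences.
- CI half-width: t(0.975, 14) × S / √15 = 2.145 × S / 3.873 = 0.554 S.
- Band half-width: 1.96 S.
- Ratio: 1.96 / 0.554 = 3.54, whatever S is.

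SAP 1.4.4 does not say whether the differences are between subject means or between single breaths. With breath-level differences and SDs of 1 for γ and ε in both methods, the band is 1.96 × √(2 + 2) = 3.92. That is 3.92 / 0.858 = 4.6 times the CI half-width in step 4, and this ratio does depend on the SDs.

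**4. Illustrative width of the missing A-D interval.** Take SDs of 1 cmH2O for γ and ε, 5 breaths and 15 patients.
- γ_ij in both methods, as the ρ_inter formula implies: S = √(2 × 1 + 2 × 1/5) = 1.549. The half-width is 0.554 × 1.549 = 0.86 cmH2O and the band is ± 3.04.
- γ_ij in method 2 only, as its verbal definition implies: S = √(1 + 2 × 1/5) = 1.183. The half-width is 0.66 cmH2O and the band is ± 2.32.

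SAP 1.4.3 is inconsistent on which reading applies. Its distribution line also gives γ_ij the variance symbol of α_i; I have read it as σ_γ².

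**5. Cost of adjusting for order when there is no order effect.** In a simulation with the first reading of γ and four positions, the mean A-D half-width was 0.842 unadjusted and 0.881 with a linear position term. The ratio is 0.881 / 0.842 = 1.05, about 5% wider.

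**The case against.** - **The offset is not hidden.** This stands. A reader might infer that the SAP looks at nothing but consistency. It does not: β_j is estimated when the model is fitted, the table gives each maneuver's mean, every pair is plotted, and A-D has a Bland-Altman plot. If that plot uses subject means, its mean and SD give an unadjusted CI in one line. What is absent is a planned interval and the order adjustment. The table by maneuver does not supply the SD of the paired differences.
- **The study is descriptive and has no margin.** True, but an estimate with a CI is a descriptive output, and the protocol specified it.
- **The SAP matches its own aim.** Section 1.4.3 does answer the pairwise-consistency aim in 1.1.1. That aim is narrower than the protocol's, and the visible text does not say why.
- **The departure may be explained elsewhere.** A reader might infer an unexplained change. The documents do not support that, because SAP material before section 1 was not available.
- **Randomising order is protection enough.** It removes order bias in expectation, though not chance imbalance among 15 patients. A reader might also infer that order effects will distort the results, but the documents give no evidence of drift. Drift would tend to lower ρ_inter, so it would not create false similarity. A linear term helps only if drift is roughly linear: with a 2 cmH2O effect confined to the middle positions, the half-width was 1.23 unadjusted and 1.29 with the linear term. The case for adjustment rests on the protocol's commitment.

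**Conclusion.** The point holds as a departure from protocol section 10. The SAP plans no CI for any mean difference between methods and no use of the randomised order, and the statistic it relies on for each pair cannot register a constant offset. These conclusions follow from the text and the formula and need no assumed values. The 3.54 ratio for the mislabelled band needs only 15 patients and differences of subject means. The 0.86 and 0.66 cmH2O half-widths are illustrations resting on assumed SDs and on how γ_ij is read.

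A reader might infer that adding an A-D interval restores the protocol's analysis. It does not. A and D are both airway measures, whereas the protocol's reference is transpulmonary, and no variable in SAP 1.3.1 provides it. The reference has to be settled first.

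The defect is worth fixing but does not undermine the data: the measurements needed are collected under protocol section 9, and β_j is already in the model.

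**What to change.** 1. **Reference.** Reconcile protocol section 9 with SAP 1.1.1. Either state in the SAP that the protocol's contrast is replaced, and why, or restore it by adding the transpulmonary volume-control measure to SAP 1.3.1 and taking differences from it.
2. **Mean difference.** In 1.4.3, report β_j with a 95% CI from the Aim 2 model, adjusted for position in the randomised order. Do this for A-D, or for each method on the same scale as the reconciled reference. Leave out pairs with B, because P0.1 measures effort. Include pairs with C only if predicted ΔP_L is treated as comparable. Use a t-based interval (Satterthwaite or Kenward-Roger degrees of freedom). A percentile parametric bootstrap like the one planned for the variances would cover about 93% at 15 patients, since P(|t14| < 1.96) = 0.930.
3. **Order.** Add the sequence variable to SAP 1.3.1 and prespecify the form of the position term. State how position is assigned: protocol section 8 shows four letters, section 9 lists maneuvers a to e, SAP A and B both come from protocol maneuver a, and SAP C draws on b and c.
4. **Bland-Altman.** In 1.4.4, call the 1.96 SD band limits of agreement only, and say whether it uses subject means or single breaths.

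**Cost.** SAP wording, merging the order list that protocol section 8 says is made before study start, and a few output lines. If there is no order effect, a linear position term widens the interval by about 5% in the illustrative simulation.
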